7.1.7 Temporary discontinuation

Temporary discontinuation of VH4524184/placebo is not allowed in this study.

7.1.8 Rechallenge

Rechallenge with VH4524184/placebo is not allowed in this study.

7.1.8.1 Study Intervention Restart or Rechallenge After Liver Stopping Criteria Are Met

Study intervention restart or rechallenge after liver chemistry stopping criteria are met by any participant in this study are not allowed.

7.2 Participant discontinuation/withdrawal from the study

A participant may withdraw from the study at any time at the participant's own request for any reason (or without providing any reason).

A participant may be withdrawn from the study at any time at the discretion of the investigator for safety, behavioral, or adherence reasons. Discontinuing from the study for safety reasons should be infrequent.

As described in Section 7.1, participants who meet a safety stopping criteria or who discontinue study intervention due to a safety reason, should remain in the study, continue to comply with all other aspects of the protocol (such as starting the first dose of standard of care ART on Day 10) and be followed according to the SoA (Section 1.3) to the EOS as defined in the protocol.

Participants will not be replaced if the reason for discontinuation from the study is due to a safety concern.

If participants prematurely discontinue the study for non-safety reasons prior to Day 10 (primary endpoint), additional replacement participants may be enrolled at the discretion of the sponsor and investigator. These replacement participants will be assigned to the same treatment sequence and same dose as the corresponding participant who prematurely discontinued from the study.

Investigators will attempt to contact participants who do not return for scheduled visits or follow-up.

At the time of discontinuing from the study, if possible, an early discontinuation visit should be conducted, as shown in the SoA. See SoA for data to be collected at the time of study discontinuation and follow-up and for any further evaluations that need to be completed. The participant will be permanently discontinued from the study intervention and the study at that time.

All data and samples collected up to and including the date of withdrawal of/last contact with the participant will be included in the study analyses. If the participant withdraws consent for disclosure of future information, the sponsor may retain and continue to use any data collected before such a withdrawal of consent.

If a participant withdraws from the study, the participant may request destruction of any samples taken and not tested, and the investigator must document this in the site study records.

The primary reason for participant discontinuation/ withdrawal from the study will be documented in the eCRF based on the list below:

Reasons	Additional items/Sub-reasons
AE	
Lack of efficacy	
Lost to follow-up	Subject Relocated Subject was Incarcerated Other, specify Unknown
Participant Reached Protocol-Defined Stopping Criteria	Specify
Physician Decision	Specify
Pregnancy	
Protocol Deviation	Specify
Site Terminated by Sponsor	
Study terminated by Sponsor	
Withdrawal by Participant	Burden of Procedure Participant Relocated Pursue Alternative Treatment COVID-19 Pandemic Other
Other	Specify
Death	

Participants who are withdrawn from the study because of AEs/SAEs must be clearly distinguished from participants who are withdrawn for other reasons. Investigator will follow participants who are withdrawn from the study due to an AE/SAE until the event is resolved (see Section 10.3.6.5).

7.3 Lost to follow-up

A participant will be considered lost to follow-up if the participant repeatedly fails to return for scheduled visits and is unable to be contacted by the study site.

The following actions must be taken if a participant fails to return to the clinic for a required study visit:

- The site must attempt to contact the participant and reschedule the missed visit as soon as possible, counsel the participant on the importance of maintaining the assigned visit schedule and ascertain whether the participant wishes to and/or should continue in the study.
- Before a participant is deemed lost to follow-up, the investigator or designee must make every effort to regain contact with the participant (where possible, 3 telephone calls, and if necessary, a certified letter to the participant's last known mailing

address or local equivalent methods). These contact attempts should be documented in the participant's medical record.

- Should the participant continue to be unreachable, the participant will be considered to have withdrawn from the study.
- Site personnel, or an independent third party, will attempt to collect the vital status of the participant within legal and ethical boundaries for all participants randomized, including those who did not get study intervention. Public sources may be searched for vital status information. If vital status of the participant is determined as deceased, this will be documented and the participant will not be considered lost to follow-up. Sponsor personnel will not be involved in any attempts to collect vital status information.

8 STUDY ASSESSMENTS AND PROCEDURES

- Study procedures and their timing are summarized in Section 1.3. Protocol waivers or exemptions are not allowed.
- Adherence to the study design requirements, including those specified in the SoA, is essential and required for study conduct.
- All screening evaluations must be completed and reviewed to confirm that potential participants meet all eligibility criteria. Subjects who have signed informed consent but are not eligible to proceed should be recorded in the eCRF with a status of 'screen failure'.
- Procedures conducted as part of the participant's routine clinical management (e.g., blood count) and obtained before signing of the ICF may be utilized for screening or baseline purposes provided the procedures met the protocol-specified criteria and were performed within the timeframe defined in the SoA.
- In the event of a significant study-continuity issue (e.g., caused by a pandemic), alternate strategies for participant visits, assessments, study intervention distribution and monitoring may be implemented by the sponsor or the investigator, as per local health authority/ethics requirements.
- Safety/laboratory/analyte results (e.g., HIV RNA (viral loads) that could unblind the study will not be reported to investigative sites or other blinded personnel until the study has been unblinded.
- The maximum amount of blood collected from each participant over the duration of the study or any 56 day period while enrolled in the study, including any extra assessments that may be required, will not exceed 500 mL.
- Repeat or unscheduled samples may be taken for safety reasons or for technical issues with the samples.
- Pharmacokinetic results that could unblind the study will not be reported to investigative sites or other blinded personnel.
- **Order of assessments:** Assessment procedures should occur in the following order:

1. ECG (if applicable)
2. Vital sign assessment
3. CSSRS
4. Blood draws; (HIV RNA to be collected at same time as pre-dose PK sample [with no preference as to which is drawn first])
5. **CCI** [REDACTED]

- All Day 10 assessments must be completed prior to administration of the first dose of standard of care ART.

8.1 Administrative and baseline procedures

8.1.1 Collection of demographic data

Record demographic data such as year of birth, sex at birth, current sex, current gender identity, race, and ethnicity in the participant's eCRF.

Collection of these demographic data is necessary to assess and monitor the diversity of the trial participants, and to determine if the trial participants are truly representative of the impacted population.

8.1.2 Medical/vaccination history

Obtain the participant's medical and disease history by interviewing the participant and/or review of the participant's medical records. Record any pre-existing conditions (including reasons for taking concomitant medications), signs and/or symptoms present prior to the first dose of study intervention in the eCRF.

8.2 Efficacy assessments

Planned timepoints for all efficacy assessments are provided in the SoA (Section 1.3).

8.2.1 Quantitative HIV-1 RNA

Plasma for quantitative HIV-1 RNA will be collected at timepoints listed in Section 1.3. An HIV-1 RNA PCR assay (Cobas HIV-1) with a linear range of 20 to 10,000,000 copies/mL will be used. Details concerning the handling, labeling and shipping of these samples to the central laboratory will be supplied in the Laboratory Manual.

8.2.2 Lymphocyte Subsets by Flow Cytometry

Blood samples will be obtained from each participant for the analysis of lymphocyte subsets by flow cytometry at the timepoints listed in Section 1.3. Details concerning the handling, labeling and shipping of these samples will be supplied in the Central Laboratory Manual. Refer to the List of Clinical Laboratories and Key Vendors document for laboratory names and addresses of the clinical laboratories used in this study.

8.3 Safety assessments

Planned timepoints for all safety assessments are provided in the SoA.

8.3.1 Physical examination/history directed physical examination

- A complete physical examination will include, at a minimum, assessments of the skin, cardiovascular, respiratory, gastrointestinal, and neurological systems.
- A brief physical examination will include, at a minimum, assessments of the skin, lungs, cardiovascular system, and abdomen (liver and spleen). At the discretion of the investigator, a brief physical examination may be made a complete physical examination.
- Investigators should pay special attention to clinical signs related to previous serious illnesses.
- Height and weight measurements will be used to calculate BMI.

8.3.2 Vital signs

- Body temperature, pulse rate, respiratory rate, and blood pressure will be recorded (before blood collection for laboratory tests).
- Body temperature will be assessed as per site's standard practice and should be measured at the same location throughout the study.
- Blood pressure and pulse measurements should be preceded by at least 5 minutes of rest for the participant in a quiet setting without distractions. Blood pressure and pulse measurements will be assessed in a semi-supine position with a completely automated device. Manual techniques will be used only if an automated device is not available.
- If abnormalities in pulse or blood pressure are noted, repeat recordings should be measured in triplicate, at least 1 minute apart. The average of the 3 readings will be recorded in the eCRF.

8.3.3 Electrocardiograms

- 12-lead ECG(s) will be obtained as outlined in the SoA (see Section 1.3) using an ECG machine that automatically calculates the heart rate and measures PR, QRS, QT, and [QTc] intervals. Each ECG recording will be obtained after the participant has been in a semi-supine position for at least 5 minutes. The ECG should be read locally. Contact the VH medical monitor with any concerns.
- If clinically indicated, the ECG should be repeated twice more (triplicate obtained) with recordings obtained as closely as possible in succession. Data from the average of 3 ECGs will be used for any action taken. Triplicate ECGs should be obtained if the investigator determines an ECG abnormality is clinically significant or if the investigator is unable to determine the significance of abnormalities relating to rate, rhythm, or intervals (including prolongation of the QT interval),
- Refer to Section 7.1.3 for QTc stopping criteria for further details.

8.3.4 Clinical safety laboratory tests

- See Section 10.2 for the list of clinical laboratory tests to be performed in accordance with lab manual and the SoA (Section 1.3).
- The investigator must review the laboratory results, document this review, and record any clinically significant changes occurring during the study as an AE. The laboratory results must be retained with source documents.
- Abnormal laboratory findings associated with the underlying disease are not considered clinically significant unless judged by the investigator to be more severe than expected for the participant's condition.
- All laboratory tests with values considered clinically significantly abnormal from dosing of the study intervention until EoS visit (i.e., Day 38) should be repeated until the values return to normal or baseline or are no longer considered clinically significant by the investigator or medical monitor.
 - In the absence of a diagnosis, abnormal laboratory findings assessments or other abnormal results the investigator considers clinically significant will be recorded as an AE or SAE, if they meet the definition of an AE or SAE (refer to Section 10.3.1 and Section 10.3.2).
 - If clinically significant values do not return to normal/baseline within a period of time judged reasonable by the investigator, the etiology should be identified, and the sponsor notified.
 - If laboratory values from non-protocol-specified laboratory tests performed at the institution's local laboratory require a change in participant management or are considered clinically significant by the investigator (e.g, SAE or AE), then the results must be recorded.

8.3.5 Pregnancy testing for participants of childbearing potential

- Refer to Section 5.1 Inclusion Criteria for pregnancy testing entry criteria.
- Refer to Section 1.3 (Schedule of Activities) for pregnancy testing schedule.
- POCPB must perform a pregnancy test before the administration of any dose of study intervention during the Monotherapy Period. Pregnancy testing will continue throughout the Follow-up Period.
- Serum samples will be sent for pregnancy testing for the Screening Visit. At the Day 1 Visit (before start of study treatment), a urine test must be used to confirm pregnancy status prior to administration of study treatment.
- Pregnancy testing must be done even if the participant is menstruating at the time of the study visit. The study intervention may only be administered if the pregnancy test is negative.
- Additional serum or urine pregnancy tests may be performed, as determined necessary by the investigator or required by local regulation, to establish the absence of pregnancy at any time during the participant's participation in the study.

- Refer to Section 8.4.5 (Pregnancy reporting) for pregnancy reporting requirements and information on study continuation for participants who become pregnant during the study.

8.3.6 Suicidal ideation and behavior risk monitoring

Although VH4524184 is not being developed for a neurologic or psychiatric condition, participants will be excluded based on any pre-existing psychiatric condition (including assessment using the CSSRS). Depression (including suicidal ideation and behaviors, particularly in patients with a pre-existing history of depression or psychiatric illness) are adverse drug reactions **CCI**.

Participants receiving VH4524184 should be monitored appropriately and observed closely for SIB or any other unusual changes in behavior. Participants who experience signs of SIB should undergo a risk assessment. All factors contributing to SIB should be evaluated and the participant should not receive any additional doses of VH4524184.

Assessment of suicidal ideation and behavior / intervention emergent suicidal ideation and behavior will be monitored using the electronic CSSRS (see SoA, Section 1.3 for details) at Screening, on Day 10 and the final follow-up visit, as well as at early termination, if applicable. As described in Section 7.1, any positive (abnormal) CSSRS response indicating SIB, or SIB reported by the participant at any other time during the study, will result in withdrawal of study drug. In either case (screening or post-dose) of positive (abnormal) response confirmed by the investigator, the PI/SI will arrange for urgent specialist psychiatric evaluation and management.

The definitions of behavioral suicidal events used in this scale are based on those used in the Columbia Suicide History Form [Posner, 2007]. Questions are asked on suicidal behavior, suicidal ideation, and intensity of ideation. Screening visit questions will be in relation to lifetime experiences and current experiences (within the past 2 months) and all subsequent questioning in relation to the last assessment. A response graded as level 4 or 5 for suicidal ideation and/or any positive response to questions addressing suicidal behavior is considered a positive CSSRS which then should be confirmed by the investigator following an interview with the participant.

Participants who experience a confirmed positive CSSRS, or who report SIB at any other time during the study, should have study drug withdrawn and should be referred for further medical assessment and treatment as appropriate. The participant should be encouraged to continue in the study and be followed as per the SoA. (See Section 1.3).

Additionally, the investigator will collect information using the PSRAE eCRF form in addition to the AE (non-serious or SAE) eCRF form on any subject that experiences a possible suicidality-related AE while participating in this study. This may include, but is not limited to, an event that involves suicidal ideation, a preparatory act toward imminent suicidal behavior, a suicide attempt, or a completed suicide. The investigator will exercise his or her medical and scientific judgment in deciding whether an event is possibly suicide related. PSRAE forms should be completed and reported to VH/GSK within 1 week of the investigator diagnosing a possible suicidality-related AE.

8.3.7 Study pausing rules

Participant safety will be continuously monitored by the Medical Monitor, designated Safety Lead (or delegate), throughout the study. Pertinent findings and conclusions are shared with the product's SRT for review of the overall benefit-risk profile of the product. The Sponsor's governance group, VSLC will review data and the team's recommendation when any pausing/stopping rules are met. The VSLC is comprised of senior representatives from various departments, including clinical development, safety, toxicology, pharmacovigilance, epidemiology, and medical affairs. The VSLC will govern whether enrollment may be resumed/modified, a given treatment arm will be stopped, or the study stopped. (See Section 10.1.6 for more details on VSLC)

The following study pausing criteria would be applied:

- Death of a participant, regardless of investigator's assessment of causality
- Any Grade 4 event or an SAE, regardless of its severity, that is considered to be clinically significant and reasonably attributable to dosing with VH4524184 in the opinion of the investigator or the Sponsor.
- Any Grade 3 or higher AE (of the same type) in 2 or more participants, leading to the decision to withdraw from the study (by the investigator), assessed by the investigator as reasonably attributable to VH4524184.
- Any Grade 2 or higher rash with evidence of systemic involvement (e.g., fever, liver transaminase elevation and/or eosinophilia) that the investigator considers reasonably attributable to VH4524184 occurring in two or more participants.
- Any Grade 4 laboratory abnormality (of the same type) or Grade 3 laboratory abnormalities (of the same type, with the exception of an asymptomatic Grade 4 lipid abnormalities or CPK increase) that the investigator considers reasonably attributable to VH4524184, in two or more participants.
- Any participant meeting liver stopping criteria that the investigator considers reasonably attributable to VH4524184.
- Any participant meeting QTc stopping criteria that the investigator considers reasonably attributable to VH4524184.
- Clinically significant arrhythmia in two or more participants.

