7 DISCONTINUATION OF STUDY INTERVENTION AND PARTICIPANT DISCONTINUATION/WITHDRAWAL

7.1 Discontinuation of study intervention

‘Discontinuation’ of study intervention refers to any participant who has not received all planned doses of the study intervention. In rare instances, it may be necessary for a participant to permanently discontinue study intervention.

If study intervention is permanently discontinued, the participant should remain in the study, continue to comply with all other aspects of the protocol (such as starting the first dose of standard of care ART on Day 10) and be followed according to the SoA (Section 1.3) to the EOS as defined in the protocol.

If participants prematurely discontinue study treatment prior to Day 10 (primary endpoint), participants may be replaced at the discretion of the Sponsor in consultation with the investigator.

Participants will not be replaced if the reason for discontinuation from the study treatment is due to a safety concern which the investigator considers reasonably attributable to study treatment e.g., when a participant meets stopping criteria. Refer to Section 7.1.2 (Liver chemistry stopping criteria), Section 7.1.3 (QTc stopping criteria) and Section 7.1.5 (Suicidal ideation and behavior) and Section 7.1.6 (Hypersensitivity reactions).

A participant may be discontinued from the study intervention at any time if any of the protocol individual stopping criteria are met:

- Emergence of any positive (abnormal) CSSRS response, or participant report of suicidal ideation and behavior at any time during the study, confirmed by the investigator or a clinician (or qualified designee) during the monotherapy period.
- Pregnancy
- \geq Grade 3 AE (or clinically significant laboratory abnormality) suspected to be related to VH4524184.
- An SAE, regardless of its severity, that is considered to be clinically significant and reasonably attributable to dosing with VH4524184, in the opinion of the Investigator.
- A grade ≥ 2 rash with concurrent fever with or without concurrent elevations in liver biochemistry reasonably attributable to dosing with VH4524184, in the opinion of the Investigator.
- Emergent medical condition that is judged by the Investigator as to jeopardize the subject’s safety if he or she continues to receive the study drug.

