7.1.6 Hypersensitivity reactions Stopping Criteria

Any participant with Grade ≥ 3 allergic reactions that are considered to be possibly or probably related to the IP will be withdrawn from the study. Participants should be treated as clinically appropriate and followed until resolution of the AE.

Participants may continue IP for Grade 1 or 2 allergic reactions at the discretion of the Investigator. The participant should be advised to contact the Investigator immediately if there is any worsening of symptoms or if further systemic signs or symptoms develop. Antihistamines, topical corticosteroids, or antipruritic agents may be prescribed.

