10.1.6 Committee structure

Participant safety will be routinely monitored by the VH medical monitor and the GSK safety lead(s). Pertinent findings and conclusions are shared with the product's SRT for periodic review of the overall benefit risk profile of the product and escalated, as necessary to VSLC.

An SRT is in place for each VH product. It comprises of a global cross-functional VH/GSK team responsible for the ongoing assessment of benefit-risk for a product. The SRT contribute to the continual blinded assessment of incoming new efficacy, safety and PK information. An external data and safety monitoring committee is not utilized in this study due to the relatively small size and early phase of the trial. This is further supported by the lack of significant safety findings from the available pre-clinical toxicity studies and preliminary clinical study of VH4524184.

VSLC is a governance group that will review data and the team's recommendation when any pausing/stopping rules are met. The VSLC will govern whether enrollment may be resumed/modified, a given treatment arm will be stopped, or the study stopped. The VSLC is comprised of senior representatives from various departments, including clinical development, safety, toxicology, pharmacovigilance, epidemiology, and medical affairs.

ViiV Healthcare has transferred certain sponsor obligations (e.g., clinical operations, study intervention management, data management, statistics and programming, clinical pharmacology and modelling and simulation, regulatory, pharmacovigilance, etc.) to GSK who are supporting VH in the conduct of this study.

Refer to the List of Clinical Laboratories and Key Vendors document for the names and addresses for the clinical laboratories, contractors and subcontractors used by VH in this study.

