4.3.2.1. Adverse events analyses

AEs will be tabulated using Medical Dictionary for Regulatory Activities (MedDRA) preferred terms and graded by the investigator according to the Division of AIDS (DAIDS) Criteria Version 2.1.

The number and percentage of participants reporting AEs during the monotherapy period will be summarised using the following categories and subcategories:

- AEs
 - Overall
 - By System Organ Class and Maximum Grade
- AEs leading to permanent discontinuation of study treatment
- AEs leading to withdrawal from study
- Drug-related AEs
 - Overall
 - By Maximum Grade
- Drug-related Non-serious AEs
- Common ($\geq 5\%$) non-Serious AEs
- SAEs by System Organ Class and Maximum Grade
- Drug-related SAEs

The Common ($\geq 5\%$) non-Serious AEs display will also include the number of events of an AE.

Selected displays from the above list will be repeated for AEs with onset during the follow-up period and during either the monotherapy or the follow-up period. AEs with onset in the monotherapy period which continue in the follow-up period will only be included in AE summaries for the monotherapy period. See OPS for the exact AE tables to be repeated for follow-up and monotherapy + follow-up.

A listing of all AEs will be provided. All planned AE displays are provided in the OPS document.

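### The 8.3.7 pausing rule for repeated, related Grade 3 or higher AEs counts only withdrawals from the study, but 7.1 and 7.2 ask sites to stop drug and keep such participants in the study, so the trigger would seldom be met

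*Protocol*

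**What the plan says.** **The pausing rule.** Protocol 8.3.7 lists: "Any Grade 3 or higher AE (of the same type) in 2 or more participants, leading to the decision to withdraw from the study". The bullet adds that the decision is the investigator's and that the AE is assessed as reasonably attributable to VH4524184. When a pausing rule is met, the VSLC reviews the data and decides whether enrolment resumes or changes, an arm stops, or the study stops.

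**What happens to the individual.** Among the criteria on which a participant may be taken off study drug, Protocol 7.1 includes Grade 3 and above: "Grade 3 AE (or clinically significant laboratory abnormality) suspected to be related to VH4524184". On what follows, 7.1 says: "If study intervention is permanently discontinued, the participant should remain in the study". Protocol 7.2 repeats it: "participants who meet a safety stopping criteria or who discontinue study intervention due to a safety reason, should remain in the study". It also says: "Discontinuing from the study for safety reasons should be infrequent".

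**An exception.** For related Grade 3 or higher allergic reactions, Protocol 7.1.6 says that participants with reactions "considered to be possibly or probably related to the IP will be withdrawn from the study".

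**The analysis.** SAP 4.3.2.1 has a category for "AEs leading to permanent discontinuation of study treatment" and a separate one for AEs that led to leaving the study.

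**The concern.** The pausing rule depends on an outcome that the participant-level rules tell sites to avoid. If two participants have the same related Grade 3 AE, the expected course under 7.1 and 7.2 is that both stop drug and both stay in follow-up. Neither case then meets the 8.3.7 condition.

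The study has no external data monitoring committee, and 8.3.7 is what sets the point at which the VSLC must review the data. If a trigger cannot readily be met, a defined pause becomes a discretionary one for that group of AEs. Sites and sponsor may also read the same bullet differently. Depression shows why this matters: Protocol 2.3.1 names it as a potential risk, yet 8.3.7 has no psychiatric bullet. Two related, non-serious Grade 3 depression AEs could stop drug in both participants and set off no defined pause.

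**Working it through.** The documents state no operating characteristic for this rule, so there is no figure to reproduce. The point rests on the text. The arithmetic only shows how much the wording could matter.

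**Step 1: does the protocol treat stopping drug and leaving the study as the same thing?** Mostly not.
- 7.1.3 withdraws participants who meet the QTc criteria from study treatment.
- 7.1.5 and 8.3.6 withdraw drug after a confirmed positive suicidality assessment and encourage the participant to continue in the study.
- 7.1.1 and 7.2 have separate lists of reasons for the two events.
- 8.4 names intervention and study as separate things that an AE may cause a participant to discontinue.
- SAP 4.3.2.1 tabulates them separately.
- 7.1.6 blurs them: it sits under the heading on stopping intervention but speaks of leaving the study.

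**Step 2: which AEs lose their trigger?** Take related Grade 3 or higher AEs and remove those that another 8.3.7 bullet or 7.1.6 already handles.
- A single attributable, clinically significant Grade 4 event or SAE pauses the study with no withdrawal condition. This includes a Grade 3 AE that is serious because of hospitalization.
- Laboratory abnormalities, rash with systemic involvement, liver, QTc and arrhythmia events have their own bullets, also without that condition.
- Related Grade 3 or higher allergic reactions leave the study under 7.1.6, so they count.

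What remains is related, non-serious, non-laboratory, non-allergic Grade 3 AEs of the same type in two or more participants.

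**Step 3: illustration of size.**

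Inputs:
- n = 18 active participants in Part 1 (3 cohorts × 6, Protocol 4.1).
- p = probability that an active participant has the qualifying AE and stops drug (assumed).
- w = share of those cases that count under the rule (assumed). w = 1 means that every drug stop counts. w = 0.10, with range 0 to 0.25, stands for the few who also leave the study.
- One value of p is anchored to study 218803, where 63 participants had received VH4524184 and the visible text reports no AE above moderate. The one-sided 95% upper bound from 0 of 63 is 1 − 0.05^(1/63) = 0.046.

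Formula, with q = p × w: P(at least 2 of 18) = 1 − (1 − q)^18 − 18q(1 − q)^17.

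Example at p = 0.05:
- w = 1, q = 0.05: 1 − 0.3972 − 0.3763 = 0.226 (0.2265 before rounding).
- w = 0.10, q = 0.005: 1 − 0.91372 − 0.08265 = 0.004.

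| p | w = 1 | w = 0.25 | w = 0.10 | w = 0 |
|---|---|---|---|---|
| 1% | 0.014 | 0.001 | 0.0002 | 0 |
| 4.6% | 0.200 | 0.018 | 0.003 | 0 |
| 5% | 0.226 | 0.021 | 0.004 | 0 |
| 10% | 0.550 | 0.073 | 0.014 | 0 |

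**Limits of the table.**
- Nothing in the documents supports any value of w.
- The 4.6% bound is for any Grade 3 or higher AE, whereas the rule needs AEs of the same type. Using it as p therefore overstates how often the rule fires.
- p is not restricted to the group left over in Step 2, so the apparent loss is overstated too.
- 218803 enrolled healthy volunteers.

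**The case against.** **The wording may simply mean stopping drug.** Besides 7.1.6, the replacement rules use the terms loosely: 4.1 speaks of discontinuing the study where 7.1 speaks of study treatment. On that reading the rule works and there is no loss. This is a fair possibility. But 8.3.7 does not say so, and most of the protocol and the SAP keep the two events apart, so it does not remove the ambiguity.

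**Study withdrawal for safety is a real route.** 7.2 lets the investigator withdraw a participant for safety at any time, the reasons listed for leaving include AE, and 7.1 and 7.2 say should, not must. This stands. A reader might infer that the rule can never fire, and the documents do not support that. Seldom is the right word. Nor is stopping drug automatic, since 7.1 says that a participant may be discontinued.

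**Repeated cases would still be seen.** A reader might also infer that repeated Grade 3 AEs would go unreviewed. The documents say otherwise. The Medical Monitor, the Safety Review Team and the sponsor review safety data throughout, singly and collectively, and under 10.1.6 findings are "escalated, as necessary to VSLC". This stands. What is lost is the defined trigger.

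**The group is small.** Functional Grade 3 already implies that intervention or hospitalization is indicated, and some such events would be classed as SAEs by medical judgment. This narrows the group further but does not empty it.

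**A plain swap of terms would open a new gap.** 7.1 defines discontinuation as not having received all planned doses, so an AE that starts after the last dose cannot lead to it. Counting only drug discontinuation would drop late AEs that the present wording can count. This is correct, and it decides the form of the fix.

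**Conclusion.** The concern holds in a limited form. As written, the 8.3.7 trigger for repeated, related Grade 3 or higher AEs depends on study withdrawal, which 7.1 and 7.2 discourage. It would therefore seldom be met for related Grade 3 AEs that are non-serious, non-laboratory and non-allergic. The other triggers in 8.3.7 are unaffected.

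The conclusion rests on the literal reading of 8.3.7 and on sites following 7.1 and 7.2. On the looser reading the fault is ambiguity only. No firing rate can be claimed. Under the assumed inputs, rates of 5% or less are the more plausible ones, and there the chance of a pause falls from at most about 0.23 to at most about 0.02 across the assumed range of w. The change is worth making because it is cheap and concerns participant safety. Confidence is medium, given the possible looser reading.

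**What to change.** Make two wording changes together.

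1. In Protocol 8.3.7, replace the study-withdrawal condition with: leading to discontinuation of study intervention or withdrawal from the study (by the investigator). The second limb keeps AEs that start after the last dose within the rule.
2. In Protocol 7.1.6, say that the participant is withdrawn from study treatment, to match 7.1 and 7.2. Made alone, this change would widen the gap, because related Grade 3 or higher allergic reactions would then also stop counting towards the rule.

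The same-type, two-participant and attribution conditions stay. AEs that lead neither to stopping drug nor to leaving the study still do not count. No new data, tables, unblinding or committee are needed. The cost is that the rule may fire somewhat more often, and each pause needs a VSLC review. One small trade remains: after the 7.1.6 change, an allergic reaction that starts after the last dose would count under this bullet only if the investigator chose to withdraw the participant from the study.
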